3.2. Secondary Objectives

- to study if early intervention with Zilucoplan® is safe (number of AEs/SAEs)
- to study if early intervention with Zilucoplan® affects clinical outcome defined by duration of hospital stay, 6-point ordinal scale, time to defervescence, supplemental oxygen use and SOFA score
- to study if early intervention with Zilucoplan® affects progression to mechanical ventilation and/or ARDS and duration of ICU stay
- to study if early intervention with Zilucoplan® affects the rate of nosocomial infection
- to study if treatment with Zilucoplan® has a favourable effect on long term at follow up 12-22 weeks post-randomization
- to study if treatment with Zilucoplan® affects all-cause mortality rate at day 28 and at 12-22 weeks post-randomization

4. End Points + Time Points

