should continue prophylactic antibiotics once daily for 14 days after the last dose of Zilucoplan®. If the participant is discharged before D28, daily prophylactic antibiotic treatment will be taken orally until 14 days after last dose of Zilucoplan®. For Arm B, the 28-day assessment period comprises SOC treatment up to 28 days post randomization or hospital discharge, when the D28 nominal day procedures. Arm B will only have 1 week of IV prophylactic antibiotics once daily, starting on D1. If hospital discharge occurs before D28 post-randomisation, both SOC and antibiotic treatment will cease and the D28 nominal day procedures will occur by telephone.

For both arms, whilst in hospital, assessments will continue on a daily basis as possible, until discharge or Day 28 is reached. If discharge is prior to D28, no daily assessments will be carried out – just the D28 telephone call.

The maximum time window for an eligible participant signing the informed consent document (and starting screening) and being randomised is 24 hours. It is assumed that first dose occurs very soon after randomisation.

An interim analysis (Interim 1) of the primary endpoints is planned after approximately half the planned number of participants have been dosed and had the opportunity to complete D15 assessments. The purpose of the interim analysis is to understand if there is already enough evidence to prompt further work on COVID-19 treatment with Zilucoplan®. There is currently no plan to stop the study based on interim results at this stage. Other endpoints may be summarised as the data allows. Safety data will also be reviewed and summarised as appropriate.

There will also be an interim analysis (Interim 2) when all participants have had the opportunity to complete D28 procedures (by phone call) to assess the primary endpoints, response rate, time to response, time to discharge and 28-day mortality, as appropriate. These analyses will enable key results to be understood as soon as possible, without compromising the study. In addition, safety will be summarised by incidence of TEAE and SAE by treatment arm. Graphs showing the time course for oxygen levels and 6-point ordinal score and Kaplan-Meier plots for time-to-event variables will be provided.

Final analyses will be carried out after all participants have either discontinued prematurely from or completed the study, by completing the follow-up visit.

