2.2.1.2 Secondary efficacy endpoint(s)

All time to event endpoints are measured from date of randomization. It is expected that there will be approximately 24 hours between randomization and dosing.

All endpoints associated with each secondary objective are listed together. The key endpoints are written in bold to be analysed/summarized at the second interim analysis when all participants have had the opportunity to complete Day 28 Procedures. Collected endpoints and their timing that may be used to derive the endpoints are listed in the third column. Alternative sources of the same information may be available and used.

There is overlap on some of the measurements across endpoints. Some may be taken once for each endpoint or taken once and used for more than one endpoint.

Details of the items in the 6-point ordinal score are provided below this table. Brief details of SOFA, are provided and further information can be obtained from the hyperlink.

Secondary Objective	Endpoint	Measurement

1) To study if early intervention with Zilucoplan® affects clinical outcome defined by duration of hospital stay, 6-point ordinal scale, time to defervescence, supplemental oxygen use, SOFA score
	
Incidents of participants reporting each severity rating in 6-point ordinal scale at D1, D6, D15 and D28
 
Change from baseline in 6-point ordinal scale to Day 6, Day 15 and Day 28 (by phone call) weeks post randomisation
 
Time to at least a 2-point improvement or discharge sustained up to D28 on the 6-point ordinal scale during 28-day assessment period
 
Percentage of participants reporting at least a 2-point improvement sustained to D28 or discharge
 
AUEC/Time using the 6-point score recorded daily – up to D15, D28 and all data recorded
 
Percentage of participants who record a 2-point improvement from baseline or discharge at D6, D15 and D28
 
Percentage of participants not deteriorating according to the ordinal scale by 1 or 2 points on D6, D15 and D28
 
6-point ordinal Scale at D6 and D15 and D28 in relation to D-Dimers and complement C5a levels at baseline
	
6-point ordinal scale measured daily up to discharge, D28 and follow-up
 
Lab values at baseline for D-Dimers and C5a

	
Change from baseline in SOFA score (https://www.mdcalc.com/sequential-organ-failure-assessment-sofa-score) to Day 6, Day 15 (or at discharge, whichever comes first)
	
SOFA score measured at D1, D6 and D15

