3 DATA ANALYSIS CONSIDERATIONS

3.1 General presentation of summaries and analyses

Statistical analysis and generation of tables, figures, participant data listings, and statistical output will be performed using SAS Version 9.1 or higher.

Descriptive statistics will be displayed to provide an overview of the study results. For categorical parameters, the number and percentage of participants in each category will be presented. The denominator for percentages will be based on the number of participants appropriate for the purpose of analysis. Unless otherwise noted, all percentages will be displayed to 1 decimal place. No percentage will be displayed for zero counts, and no decimal will be presented when the percentage is 100%. For continuous parameters, descriptive statistics will include number of participants with available measurements (n), mean, standard deviation (SD), median, minimum, and maximum.

Decimal places for descriptive statistics will always apply the following rules:

- “n” will be an integer.
- Mean, SD, and median will use 1 additional decimal place compared to the original data.
- Coefficient of variance (CV[%]) will be presented with 1 decimal place.
- Minimum and maximum will have the same number of decimal places as the original value.

Statistical tests of the primary efficacy endpoints will be presented as 2-sided p-values rounded to 4 decimal places. P-values less than 0.0001 will be presented as “<0.0001” and p-values greater than 0.9999 will be presented as “>0.9999.” Appropriate statistical models will be fit to the various data collected for the secondary objectives, as described in their respective sub-sections in Section 8 for the purposes of estimation. No p-values will be provided for the analysis of endpoints associated with the secondary objectives, rather 95% confidence limits of the results of various comparisons of interest will be provided.

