8.2 Statistical analysis of the secondary efficacy endpoint(s)

There are several secondary endpoints that cover each of the secondary objectives and a list is provided in the table listing the secondary endpoints in Section 2.2.1.2. Some of these endpoints are different derivations from the same collected data. In addition, some of the endpoints collected for one objective, may be the inputs to derivations for endpoints for the same objective or for another objective.

Data types for the secondary efficacy endpoints fall into the following main categories: continuous (for example, change from baseline (including the various ordinal categorical endpoints), number of days with 'condition'), ordinal categorical, binary ('responder' Y/N), time to event or duration of event.

Table 8.1 describes the analyses of each secondary endpoint listed in Section 2.2.1.2 and identifies which efficacy objective (2-6) the endpoint is addressing. Brief details of any derivations and analysis methods used are provided. Further details are included in the mock TFL shell document. In the event the data for some of these endpoints indicate that analysis through fitting models is not appropriate, for example too few events for a formal analysis on response or mortality rates, or time to event analyses, the analyses will not be carried out and only listings, figures and summaries provided.

Some patients may withdraw from the study or be transferred to another hospital prior to discharge through medical improvement. If data have been collected from another hospital post discharge from the first hospital, these data will be listed. This will be for variables or derived variables which would have included data from these patients. For example, duration of stay in hospital. However, for variables only including data up to a relative day prior to discharge/transfer from the first hospital, these patients will be included in the analysis/summary

for that period but set as missing for the other periods. Residual plots will be reviewed to determine any influence these participants may have had on the results.

Table 8.1

Endpoint	Derivation	Analysis

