
Objective 2
 
Time since randomization until absence of LAST fever (defined as 37.1°C or more) for more than 48 h without antipyretics (use last fever to account for possibility that participants have intermittent fever per this definition)
	
Antipyretic use in last 24 hours is collected on eCRF on every day. Use highest temperature recorded in last 24 hours, not the 7-10am temperature to identify the date when the last fever ended per definition.
 
Create variable which contains number of days between this date and date of randomisation for each participant. If a participant has had no episodes of the fever, the number of days is 0.
 
Create indicator variable (censor) to indicate if participant has recovered from the last fever at time of analysis (0=recovered, 1=fever is ongoing at time of analysis). If a participant has had no fever, (i.e. time=0), censor=0.
	
Kaplan-Meier analysis using PROC LIFETEST. Strata ACTARM.
 
Request Failure plot adjusting axis and heading titles to reflect responder and not failure
 
Output statistics:
 
Appropriate statistics from analysis as indicated in mock shell

Endpoint	Derivation	Analysis

Objective 2
 
Duration of hospital stay
 
Duration of hospital stay of survivors
	
Calculate duration of hospital stay in days (Hospital Discharge date-Hospital Admission date)
 
Create indicator variable to flag survivors
	
Summary statistics: n, nmissing, mean, SD, median, minimum, maximum
 
By treatment arm

Objective 2
 
Number of days requiring supplemental oxygenation after randomisation to Day 28 (or discharge, whichever comes earlier)
	
Number of days where Suppl O₂ = ‘Y’ from Vital parameters
	
Summary statistics: n, nmissing, mean, SD, median, minimum, maximum
 
By treatment arm

Objective 2
 
Time since randomization until improvement in oxygenation (defined as independence from supplemental oxygen) during 28 day assessment period (or discharge, whichever comes earlier)
	
Independence from supplementary oxygen means no further ‘Y’ after a ‘N’
	
Kaplan-Meier analysis using PROC LIFETEST. Strata ACTARM.
 
Request Failure plot adjusting axis and heading titles to reflect responder and not failure
 
Output statistics:
 
Appropriate statistics from analysis as indicated in mock shell

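### Duration of hospital stay is counted from admission, so the by-arm summary includes pre-randomisation days that treatment cannot affect

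*SAP*

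**What the plan says.** The Table 8.1 row for hospital stay, which covers all patients and survivors, gives this derivation: "Calculate duration of hospital stay in days (Hospital Discharge date-Hospital Admission date"). The planned output is "Summary statistics: n, nmissing, mean, SD, median, minimum, maximum" by treatment arm, with no model, covariate or Kaplan-Meier curve.

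SAP Section 2.2.1.2 sets a general start date: "All time to event endpoints are measured from date of randomization". SAP Section 8.2, listing data types, names "time to event or duration of event" and does not say whether the start-date rule extends to durations. The row next to hospital stay in Table 8.1 is worded "Number of days requiring supplemental oxygenation after randomisation to Day 28 (or discharge, whichever comes earlier"). Hypoxia days and ventilator-free days are worded in the same way.

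SAP Section 2 says Interim 2 will assess, besides the primary endpoints, "response rate, time to response, time to discharge and 28-day mortality, as appropriate". Table 8.1 has no row for time to discharge.

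Protocol Section 3.2 makes hospital stay part of a secondary objective ("clinical outcome defined by duration of hospital stay"). Protocol V6.0 Section 4.3 lists the two stay endpoints as exploratory. The SAP, which is based on protocol version 3.0, lists them as secondary.

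**The concern.** Stay from admission is the sum of days before randomisation and days after it. Only the second part can respond to treatment. The first part differs between patients for reasons unrelated to the trial arm, and the row has no covariate that would remove it. With 27 controls, the arms can differ by chance in prior stay, and that difference passes straight into the reported difference in stay.

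There is also a labelling problem. If Interim 2 reports time to discharge from randomisation, as the Section 2.2.1.2 rule implies, and the stay row counts from admission, the same discharge date is reported on two clocks without explanation.

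**Working it through.** **Start dates in the SAP**

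- From admission: duration of hospital stay (all patients, survivors). No other Table 8.1 row uses this start.
- From randomisation: days on supplemental oxygen, days with hypoxia, ventilator-free days; time to last fever, to oxygen independence, to first high-flow or ventilatory support, and to ARDS.
- Other or unstated: relative day and the primary assessment period start at first dose (Sections 3.2.1.1 and 3.2.1.2). Fever days are tied to the 28-day assessment period. The ICU-stay derivation names no start date.

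**Is prior stay bounded?** Protocol Section 7.3 allows at most 24 hours from screening to randomisation, which is not admission to randomisation. Protocol Section 6.1 limits symptom duration to 6 to 16 days, not time since admission. It also allows for delay in hospital: marker rises over 24 hours must be documented unless three criteria are already met at admission, and one enrolment route concerns patients still without laboratory confirmation after 24 hours of admission. So prior stay can be a day or more, with no stated limit.

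**Inputs.** 54 and 27 patients (Protocol Section 11.1), all assumed to contribute. The documents give no mean, SD or power for hospital stay. Their one power figure, above 85%, concerns PaO₂/FiO₂ (difference 80, SD 105). It reproduces by noncentral t (89.1% with 54 and 27; 85.5% with 49 and 24) and has no bearing here. Assumed: SD of prior stay (SDpre) 1 to 4 days; SD of post-randomisation stay (SDpost) 8 to 12 days; correlation ρ of 0, then 0.3.

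**Expected difference.** Mean prior stay is equal across arms in expectation, so it cancels from the difference in means. In a simulation of 20,000 trials (true post-randomisation means 9 and 12 days, plus a mean of 2 prior days in each arm), the mean difference was −3.00 days from either start date. Its SE was 2.18 from randomisation and 2.23 from admission.

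**Chance imbalance in prior stay.** SE = SDpre × √(1/54 + 1/27) = SDpre × 0.236.

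- SDpre 1: SE 0.24; 95% range ±1.96 × 0.236 = ±0.46 days.
- SDpre 4: SE 0.94; 95% range ±1.96 × 0.943 = ±1.85 days.

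**Inflation of the SE of the arm difference.** Ratio = √(SDpost² + SDpre² + 2ρ·SDpost·SDpre) / SDpost.

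- SDpost 12, SDpre 1, ρ 0: √145/12 = 1.003 (+0.3%).
- SDpost 10, SDpre 2, ρ 0: √104/10 = 1.020 (+2%; SE 2.36 becomes 2.40 days).
- SDpost 8, SDpre 4, ρ 0: √80/8 = 1.118 (+12%).
- At ρ 0.3 the two extremes become √152.2/12 = 1.028 (+3%) and √99.2/8 = 1.245 (+25%).

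The chance imbalance and the SE inflation are two views of the same noise and should not be added together.

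**Dilution of a relative effect.** A 25% reduction of an assumed 10-day post-randomisation stay is 2.5 days. As a share of total stay it is 2.5/11 = 22.7% with 1 prior day, 2.5/12 = 20.8% with 2, and 2.5/14 = 17.9% with 4.

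**The case against.** The other side has several sound points.

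- A reader might infer that the SAP breaks its own start-date rule. The text does not support that. The rule is worded for time-to-event endpoints, and hospital stay is planned as a duration with means and medians, no censoring variable and no Kaplan-Meier analysis. The row is out of line with its neighbours, but it is not a plain breach.
- A reader might also infer that every other time endpoint starts at randomisation. As the list of start dates shows, that is not so. What can be said is that no other Table 8.1 row starts at admission.
- Randomisation protects the all-patient difference in means from bias, and the simulation agrees. This does not carry over automatically to stay in survivors, a group selected after randomisation.
- There is little formal inference to damage. SAP Section 3.1 says "No p-values will be provided for the analysis of endpoints associated with the secondary objectives", and this row specifies no model or interval. A loss stated as patient numbers would therefore describe the efficiency of a comparison the SAP does not specify. For example, assumed SDs of 3 and 8 days raise the variance by (9 + 64)/64 − 1 = 14%. That is only about 7% in SE, and it needs zero correlation.
- Admission to discharge is the ordinary meaning of hospital stay and a legitimate descriptive measure. Discharge after randomisation also enters the ordinal-scale endpoints.

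These points limit the size of the problem. They do not remove it: treatment cannot affect the prior days, nothing bounds them, and the summary does not adjust for them.

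**Conclusion.** The point holds as a minor one. Counting from admission adds noise to the by-arm summary of stay and dilutes any relative effect, without biasing the expected all-patient difference in means. The stated sizes (a 95% chance imbalance of about ±0.5 to ±1.8 days, and an SE increase of about 0.3% to 12%) rest entirely on assumed SDs and, for the second, on zero correlation between stay before and after randomisation. Positive correlation would make the increase larger. The documents cannot narrow these ranges. Because the endpoint is descriptive and exploratory in the current protocol, no main conclusion of the trial depends on it. The change is worth making because it is free and settles which clock time to discharge uses.

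**What to change.** In Table 8.1:

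1. For the between-arm summary, define stay as discharge date minus randomisation date, for all patients and for survivors.
2. Keep total stay from admission as a separate descriptive line.
3. Report hospital days before randomisation, by arm, among the baseline characteristics in SAP Section 6.2.
4. State that time to discharge at Interim 2 starts at randomisation.

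No new data are needed. Protocol Section 9.3 already collects the day of admission, and the ARDS row of Table 8.1 already uses the randomisation date. The cost is one changed date in one derivation, one added baseline line and one clarifying sentence.

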4.2. Secondary End Points + Time Points

-To study if early intervention with Zilucoplan® is safe (number of AEs/SAEs)

-To study if early intervention with Zilucoplan® affects clinical outcome

defined by 6-point ordinal scale change between day 1 and respectively day 6, day 15 (or discharge, whichever comes first) and day 28 (by phone call). 6-point ordinal scale defined as

1. Death
2. Hospitalized, on invasive mechanical ventilation or ECMO;
3. Hospitalized, on non-invasive ventilation or high flow oxygen devices;
4. Hospitalized, requiring supplemental oxygen
5. Hospitalized, not requiring supplemental oxygen

Not hospitalized

-Number of days requiring supplemental oxygen after randomization to Day 28 (or discharge, whichever comes first)

-Number of days with fever (defined as 37.1°C or more) during 28-day assessment period

- change from baseline in SOFA score to D6, D15 (or on discharge, whichever is first)

- Time to at least a 2-point improvement or discharge sustained up to D28 on the 6-point ordinal scale during 28-day assessment period

-Incidence of nosocomial bacterial or invasive fungal infection during 28-day assessment period

Patients with viral respiratory infection are at risk of secondary bacterial infections. As part of routine clinical care, sputum or BAL samples will be collected in patients suspected of secondary bacterial

pneumonia, and checked for the presence of bacteria. Measurements of procalcitonin levels will be performed at least three times per week until day 14 or hospital discharge.

- **All-cause mortality rate at 28 days post randomization (all treated participants)**
- All-cause mortality rate at 28 days post randomization (excluding participants that required invasive mechanical ventilation or ECMO, non-invasive mechanical ventilation or high-flow oxygen devices within 24 hours prior to or after randomization)**
- All-cause mortality rate at 28 days post randomization (excluding participants that required invasive mechanical ventilation or ECMO within 24 hours prior to or after randomization)**
- All-cause mortality rate at 28 days post randomization (only including patients that required invasive mechanical ventilation or ECMO within 24 hours prior to or after randomization)**
- Incidence of patients in each category of the 6-point Ordinal Scale at follow up 12-22 weeks post-randomization**
- All cause mortality at follow up 12-22 weeks post-randomization for all treated participants**

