Upon progression of disease, need for mechanical ventilation and transfer to the ICU within the 14 day period, in patients in the active group, Zilucoplan[®] will be administered also via SC administration and at all instances presence of edema will be noted. If edema is noted, where possible drug will be administered subcutaneously in non-edematous area, with a preference for the upper leg.

At day 28 post-randomization (or within next 3 days) patients will be inquired by phone for 6-point ordinal scale, (S)AE, supplemental oxygen need (Y/N), therapy compliance (antibiotics) and concomitant medication since hospital discharge or day 15.

On a final clinical visit between week 12-22 after randomization two additional serum tubes (2 x 6 ml) and optional 2 EDTA tubes (2 x 10 ml) will be taken. Routine laboratory assessment should minimally include Ferritin, LDH, haptoglobin, D-dimers, CRP, creatinine, fibrinogen, eosinophils, lymphocytes, haemoglobin, WBC count, platelets, bilirubin, ALT and AST. Also, an arterial blood gas determination via arterial puncture will be taken. WHO-score, Lung function data (FVC, FEV₁, FRC, RV, DLCO), a 6 minute walk test and HRCT scan to assess the HRCT fibrosis score.

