
Objective 2 Percentage of participants not deteriorating according to the ordinal scale by 1 point between D1 and D6, between D7 and D15 and between D16 and D28 – not deteriorating corresponds to Stable + Responders
	
A participant is classified as Stable + Response if at no time CFB < -1. Create indicator variable (3 levels) if the relative day of START of Stable or Response falls between D1 and D6, between D7 and D15 and between D16 and D28 for each participant
	
Frequency table and percentage responders in each of the categories defined by the indicator variable, by treatment. Exact 95% confidence intervals for each percentage

Objective 2 6-point ordinal Scale at D6 and D15 and D28 in relation to D-Dimers and complement C5a levels at baseline
		
Box-whisker plot of baseline D-Dimers and complement C5a for each score (x-axis) reported on each of D6, D15 and D28

Objective 2 Change from baseline in SOFA score (https://www.mdcalc.com/sequential-organ-failure-assessment-sofa-score)
	
Change from baseline to D6 and D15 in SOFA score
	
Summary statistics for raw data and change from baseline

Endpoint	Derivation	Analysis
to Day 6, Day 15 (or at discharge, whichever comes first)		

Objective 2
 
Number of days with fever (defined as 37.1°C or more) during 28-day assessment period
	
Create indicator variable for each participant on each day where temperature is above 37.1 °C
 
Create variable with total number of days where temperature was above 37.1 °C for each participant
 
Create variable for each participant giving total number of days where temperature was recorded
	
Summary statistics to provide n, average number of days, SD, median, minimum and maximum where temperature was above 37.1 °C by treatment
 
Produce line plot of temperature over time for each patient together with average line per treatment group.
 
Temperatures are due to be taken daily until discharge – indicate the number of subjects on each day in each treatment arm

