
Objective 2
 
Number of days with hypoxia (defined as SpO₂ <93% breathing room air or the dependence on supplemental oxygen after randomisation to Day 28 (or discharge, whichever comes earlier)
	
Use SpO₂ (%) and Suppl O₂ (Y/N) from Vital parameters to derive indicator variable which flags each day where this condition holds.
 
Derive variable per participant that gives total number of days with condition
	
Summary statistics of variable with Total number of days: n, mean, SD, median, minimum, maximum
 
By treatment arm

Endpoint	Derivation	Analysis

Objective 3 Duration of ventilator free days after randomisation to Day 28 (or discharge, whichever comes earlier)
	
Use data from Vital parameters (include all days, where NIV, IV and ECMO='N')
	
Summary statistics of variable with Total number of days: n, mean, SD, median, minimum, maximum By treatment arm

Objective 3 Duration of invasive mechanical (including ECMO) and non-invasive mechanical ventilation in ventilated participants
	
Complement of above (exclude participants who are not ventilated i.e. do not include these with a duration of 0)
	
Summary statistics of variable with Total number of days: n, mean, SD, median, minimum, maximum By treatment arm

Objective 3 Time since randomization until first use of high-flow oxygen devices or non-invasive mechanical ventilation or invasive mechanical ventilation or ECMO in non-ventilated participants (i.e. excluding participants who are ventilated within 24h prior to or after randomization) during 28-day assessment period
	
Use Vital Parameter CRF and the method of supplementary oxygen variable. Use the date from this CRF to identify when first use occurred. Indicator variable to identify sub-group to be included. Censor if never used any of these ventilation methods at Day 28
	
Kaplan-Meier analysis using PROC LIFETEST. Strata ACTARM. Request Survival plot adjusting axis and heading titles to reflect progression and not response Output statistics: Appropriate statistics from analysis as indicated in mock shell

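### Table 8.1 counts oxygen, hypoxia and fever days with no rule for death, so an early death keeps a short, favourable count and the between-arm summary is distorted if mortality differs

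*SAP*

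**What the plan says.** Protocol 4.2 lists two of these counts as secondary endpoints: days with fever and "Number of days requiring supplemental oxygen after randomization to Day 28 (or discharge, whichever comes first". Hypoxia days are exploratory (Protocol 4.3). SAP 8.2, Table 8.1, carries the oxygen endpoint over as "Number of days requiring supplemental oxygenation after randomisation to Day 28 (or discharge, whichever comes earlier" and derives all three as totals of flagged days:

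- **Oxygen days:** "Number of days where Suppl O₂ = ‘Y’ from Vital parameters"
- **Hypoxia days:** "Derive variable per participant that gives total number of days with condition"
- **Fever days:** "Create variable with total number of days where temperature was above 37.1 °C for each participant"

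Each is then summarised by arm with n, mean, SD, median, minimum and maximum. The oxygen row also reports the number missing. For fever the SAP adds "Create variable for each participant giving total number of days where temperature was recorded", but the listed summary does not use that variable.

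No row mentions death, and no other section fills the gap. SAP 4.2 names death as one form of missing data and leaves its handling to each endpoint's own section. SAP 3.2.1.3 says an in-hospital death is not a discharge, so the stop at discharge does not cover it.

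**The concern.** For these counts, fewer days is better. Taken literally, the derivation gives a patient who dies on D4 while on oxygen about 4 days. A survivor weaned on D12 gets 12, and a patient who survives but needs oxygen until D25 gets 25. The worst outcome has the best number.

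The SAP deals with death in neighbouring rows of the same table. The ordinal-scale change and the AUEC carry the worst score forward after death. Time to response places deaths at D15 or D28 and censors them. Hospital stay has a survivors' version. The three day counts have nothing comparable.

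The missing count in the oxygen row does not settle the matter. If deaths were treated as missing, the row would become an undeclared comparison among survivors, so two programmers could produce different tables from the same text. At stake is whether the by-arm summaries of two protocol secondary endpoints can be read as benefit or harm when mortality differs.

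**Working it through.** The documents give no figure for these endpoints, so there is none to reproduce. The Protocol 11.1 power statement concerns PaO₂/FiO₂ only and is not affected.

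**Inputs**
- Control mortality 20%: Protocol 2.2, the figure for patients with co-morbidity.
- Drug-arm mortality 10%: assumption. The drug's only effect in this model is to prevent deaths.
- D, oxygen days accrued by a patient who dies; S, oxygen days of a patient saved from death; L, oxygen days of all other patients: assumptions.

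**Literal count**
- Control mean = 0.20·D + 0.80·L
- Drug mean = 0.10·D + 0.10·S + 0.80·L
- Drug minus control = 0.10 × (S − D). L cancels.

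The sign depends only on whether S exceeds D. With L = 10:

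| D | S | Drug | Control | Difference |
|---|---|---|---|---|
| 5 | 20 | 10.5 | 9.0 | +1.5 |
| 10 | 20 | 11.0 | 10.0 | +1.0 |
| 15 | 20 | 11.5 | 11.0 | +0.5 |
| 5 | 28 | 11.3 | 9.0 | +2.3 |
| 10 | 10 | 10.0 | 10.0 | 0.0 |
| 15 | 10 | 10.5 | 11.0 | −0.5 |

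A positive difference makes the arm with fewer deaths look worse. Over D = 5 to 15 and S = 10 to 28 the range is −0.5 to +2.3 days. With mortality 7% versus 3% the multiplier is 0.04, and the range is −0.2 to +0.9 days.

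**A fuller model.** Assume other survivors' oxygen time is lognormal with median 9 days and log-SD 0.6, capped at 28 (mean about 10.5). Assume deaths fall evenly over D3 to D25 (mean 14). Varying only the rescued patients:
- S from 18 to 28 (mean 23): control 0.20 × 14 + 0.80 × 10.5 = 11.2; drug 0.10 × 14 + 0.10 × 23 + 0.80 × 10.5 = 12.1; difference +0.9.
- S from 10 to 20 (mean 15): 0.10 × (15 − 14) = +0.1.
- S like other survivors: 0.10 × (10.5 − 14) = −0.35.

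**Days alive and oxygen-free to D28, death = 0**
- Drug minus control = 0.10 × (28 − S), which cannot be negative.
- With S averaging 23: control 0.80 × (28 − 10.5) = 14.0; drug 14.0 + 0.10 × 5 = 14.5; difference +0.5 in favour of the drug.
- With S = 20 the difference is +0.8. With S = 28 it is 0.

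**Precision with 54 versus 27.** In the fuller model with S from 18 to 28, the standard error of the difference is about 1.5 days for the literal count and about 2.0 days for days alive and free. The +0.9 shift is therefore about 0.6 standard errors.

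**The case against.** A reader might infer that any mortality difference pushes these counts the wrong way. The documents and the arithmetic do not support that. The reversal needs S > D, and neither value is documented. In the fuller model a death averages 14 oxygen days against 10.5 for other survivors, and only about 27% of deaths fall below the survivors' median. Most deaths there do not look favourable, and if rescued patients resemble other survivors the literal count moves slightly in the drug's favour.

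A reader might also infer that a trial conclusion could be reversed. Table 8.1 gives these rows descriptive statistics only. SAP 3.1 plans no p-values for secondary objectives, SAP 4.5 calls them exploratory, and 28-day mortality has its own analysis. The shift is also small against the trial's precision. All this stands and limits the weight of the point. It does not remove it: Protocol 11.2 foresees modelling of count data, SAP 3.1 promises confidence limits for secondary comparisons of interest, and a separate mortality table does not correct a distorted day count.

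Finally, a reader might call the stop at discharge a SAP error, or suppose that everything needed for a 28-day measure is already collected. Neither holds. The discharge limit on oxygen days is in Protocol 4.2. SAP 2 says daily assessments end at discharge. The D28 call described in Protocol 9.2 asks about "supplemental oxygen need (Y/N), therapy compliance (antibiotics) and concomitant medication since hospital discharge or day 15", which gives no date when oxygen stopped and no temperature or SpO₂.

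**Conclusion.** The gap is real. Followed as written, the three rows give a patient who dies early a truncated, favourable count, and no other part of the SAP corrects it. Any mortality difference can then distort the by-arm summaries. For oxygen days the direction is against the arm with fewer deaths only when S > D. With assumed mortality of 20% versus 10% the difference lies between −0.5 and +2.3 days over the inputs tried.

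All of S, D, L and the 10% mortality are assumptions. The mechanism carries over to hypoxia and fever days because they are derived the same way, but no size can be claimed for them. Because the rows are descriptive, the point concerns how secondary results will be read. It does not touch the primary analysis or the sample size.

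**What to change.** Add a supplementary derivation to Table 8.1: days alive and free of supplemental oxygen from randomisation to D28, with 0 for any death by D28. Apply the same death rule to hypoxia days (keeping their exploratory status) and to fever days. Keep the protocol-defined raw counts beside them as description, with the number of deaths shown by arm.

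State the post-discharge convention openly as an assumption:
- Patients discharged off oxygen count as oxygen-free from then on.
- For patients discharged on oxygen, the D28 yes/no answer cannot date the stop. Use a stated conservative rule, for example counting no day after discharge as free.
- Fever and SpO₂ are not observed after discharge, so freedom from them in that period is assumed.

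The cost is SAP wording and a few lines of programming. The death rule uses survival status and daily oxygen flags that the SAP already draws on for other rows. Presenting the measure as supplementary leaves the Protocol 4.2 definition unchanged. The price is a measure that combines mortality with oxygen need and is somewhat noisier (standard error about 2.0 against 1.5 days in the model above), so the components should be shown alongside it.
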